1. Protocol Title

Spinal Cord Injury Exercise and Nutrition Conceptual Engagement (SCIENCE)

2. Objectives

The specific objectives for the current proposal are to assess the impact of home-based functional electrical stimulation leg cycle ergometry plus diet (HBFESLCE + Diet) versus Diet Alone on (Primary Variables) body composition (%BF, FM and FFM), insulin sensitivity (SI), glucose effectiveness (SG), and BMR, as well as (Secondary Variables) lower extremity bone mineral density, lipid profiles, and hsCRP in adults with motor complete SCI between C4-T4. Specific objectives to be addressed in the current proposal are:

1. To determine the impact of HBFESLCE + Diet on body composition, insulin sensitivity, glucose effectiveness and BMR in adults with motor complete tetraplegia or high paraplegia above T4. Additionally, lower extremity bone mineral density & content, lipid profiles, and hsCRP will be compared before and after intervention.
2. To determine the impact of HB Diet Alone on body composition, insulin sensitivity and glucose effectiveness in adults with motor complete tetraplegia or high paraplegia. Additionally, lower extremity bone mineral density, lipid profiles, and hsCRP will be compared before and after intervention.
3. To compare the efficacy of HBFESLCE + Diet with that of HB Diet Alone relative to the parameters listed above.
4. To create a robust dataset of variables that are associated with visceral adipose tissue (VAT) to predict determinates of epicardial VAT (EAT) and abdominal VAT (AVAT) in subjects with chronic motor complete C4-T4 SCI.
5. To compare the change in epicardial adipose tissue, abdominal visceral adipose tissue, intramuscular fat, and subcutaneous adipose tissue before and after home-based FES-LCE plus diet vs. diet alone in adults with chronic motor complete C4-T4 SCI.
6. To compare changes in circulating proinflammatory adipokines before and after FES-LCE plus diet vs. diet alone in adults with chronic motor complete C4-T4 SCI.

3. Background

There are an estimated 1.5 million persons in the United States with SCI, Men 3x > Women, with ~50% having tetraplegia and recent literature would imply that more than 60% are overweight or obese by BMI standards, more than 50% are glucose intolerant,

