Forty subjects will be randomly assigned to either HBFES LCE + Diet or Diet alone. All tests will be two-sided at the $\alpha = .05$ level of significance. Effects will be reported with a point estimate and 95% confidence intervals in addition to p-values. We will examine the distributions of all measures and identify possible outliers. Dependent variables that are found to be non-normally distributed will be transformed to more closely approximate normality before analysis. Outliers will be thoroughly checked for collection or data entry errors before being used in the analysis. A linear regression model will be used to fit a model to assess the effects of exercise training (independent variable) on the change scores (post-score minus pre-score) for body composition, insulin sensitivity, glucose effectiveness, serum lipids and lower extremity bone mineral density (dependent variables). The linear regression model will have one between subjects (independent) factor, Group (HBFES LCE + Diet or Diet alone). While this model is exactly the same as a two-sample t-test for the change scores it allows for the adjustment of other explanatory variables that might have an impact on the dependent variable (i.e. age, time since injury, etc.). While we anticipate that randomization will balance out the groups with respect to covariates that may have an impact on dependent variables, if this is not the case the linear regression model for the change scores will allow for the inclusion of these covariates to adjust for the Group predictor variable, which are the real variables of interest in the study. Specific variables for body composition will include per cent and absolute BF, as well as per cent and absolute FFM mass, as determined by 4-compartment modeling. Insulin sensitivity (SI), glucose effectiveness (SG) will be the primary variables assessed from the IVGTT, and BMR will be assessed as a primary variable. Specific variables for serum lipids will include total cholesterol, HDL-C, LDL-c, triglycerides; hsCRP will be measured separately. Areal density (BMD) and bone mineral content (BMC) will also be considered secondary variables of interest.

Power calculations for Insulin Sensitivity (Si)				
Mean Diff(T2-T1) Group 1=0.0, Group 2=3.2				
$\alpha = 0.05$	Var(Time1)=Var(Time 2)=3.00	Var(Time1)=Var(Time 2)=6.00		
Sample Size	Empirical Power $\rho=0.70$	Empirical Power $\rho=0.50$	Empirical Power $\rho=0.70$	Empirical Power $\rho=0.50$

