n=10 per group	99%	98%	95%	79%

n=15 per group	100%	100%	99%	90%
n=20 per group	100%	100%	100%	97%
Mean Diff(T2-T1) Group 1=0.0, Group 2=1.6				
$\alpha = 0.05$	Var(Time1)=Var(Time 2)=3.00		Var(Time1)=Var(Time 2)=6.00	
Sample Size	Empirical Power $\rho=0.70$	Empirical Power $\rho=0.50$	Empirical Power $\rho=0.70$	Empirical Power $\rho=0.50$
n=10 per group	72%	49%	45%	31%
n=15 per group	88%	68%	57%	40%

All primary and secondary outcomes will be visually assessed (boxplots, histograms, etc.) for normality and/or continuous data will be examined with a Shapiro-Wilk test. We will use a 2-way (group x time) mixed-model analysis of variance (ANOVA) to assess group interaction. Where significant interaction effects are observed, paired and independent t-tests will be used to determine significant differences within and between groups. Alpha will be set at < 5%.

11) Provisions to Monitor the Data to Ensure the Safety of Subjects

Please refer to the attached document DSMB 0719

12) Withdrawal of Subjects

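### Objectives 1 and 2 seek the impact of each programme on its own, but with no untreated arm the trial can identify only the added effect of FES cycling over diet

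*Combined protocol and SAP*

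**What the plan says.** Section 2 opens with a between-arm aim: cycling "plus diet (HBFESLCE + Diet) versus Diet Alone on (Primary Variables) body composition", with the other primary variables following. The numbered list then splits this up.

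- Objective 1: "To determine the impact of HBFESLCE + Diet on body composition, insulin sensitivity, glucose effectiveness and BMR".
- Objective 2: "To determine the impact of HB Diet Alone on body composition, insulin sensitivity and glucose effectiveness".
- Objective 3 is the randomised contrast: "To compare the efficacy of HBFESLCE + Diet with that of HB Diet Alone relative to the parameters listed above". Objectives 5 and 6 also compare the arms.

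Objectives 1 and 2 name no comparator. For the secondary variables they state the method: bone density, "lipid profiles, and hsCRP will be compared before and after intervention". For the primary variables the before-after basis is implied, not stated.

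Section 10, Statistical methods, fixes the design: "Forty subjects will be randomly assigned to either HBFES LCE + Diet or Diet alone". It regresses change scores on group. Its closing paragraph adds a group-by-time ANOVA and says that, where the interaction is significant, "paired and independent t-tests will be used to determine significant differences within and between groups". Nothing in the documents calls within-arm results descriptive or limits how they may be read.

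**The concern.** A single-arm impact is a causal quantity: the outcome under the programme against the outcome without it. No arm goes without. Section 7 (Dietary analyses) gives both arms weekday electronic dietary coaching, weekly teleconference consultation and the same daily energy-deficit target. The diet component is therefore common to both arms and drops out of the randomised contrast.

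Objective 2 consequently has no randomised support at all. Objective 1 has it only for the increment from cycling, not for the combined programme. What remains for these objectives is before-after change, which adds to any programme effect whatever else moves over 16 weeks: passage of time, being monitored, repeat testing and some regression to the mean. At stake is a statement that diet coaching, or the combined programme, improved body composition or insulin sensitivity on evidence that cannot separate these sources.

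**Working it through.** **Inputs** (Section 10, Sample size determination). Percent body fat falls from 31.8 to 28.5 in the combined arm, a change of 3.3, against 0.06 with diet alone; the difference is 3.3 − 0.06 = 3.24. Pre and post variances are 6.25 or 12.5, the pre-post correlation is 0.70 or 0.50, there are 20 per arm, and tests are two-sided at 5%. The documents give no figure for drift; I assume 0 to 2 points and show the range.

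**Step 1: SD of change** = √(2 × variance × (1 − correlation)):
- √(2 × 6.25 × 0.30) = 1.94
- √(2 × 6.25 × 0.50) = 2.50
- √(2 × 12.5 × 0.30) = 2.74
- √(2 × 12.5 × 0.50) = 3.54

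**Step 2: reproduce the plan's power.** With two time points, the group-by-time interaction is a two-sample t-test on change scores. Its noncentrality is 3.24 / (SD of change × √(2/20)), on 38 degrees of freedom. In the least favourable setting this is 3.24 / (3.54 × 0.316) = 2.90. Power across the four settings is 99.9%, 97.9%, 95.4% and 80.6%, against 100%, 97%, 95% and 80% in the plan's table. The plan's figures are reproduced. They concern the between-arm contrast, from which drift common to both arms cancels.

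**Step 3: common drift, no arm difference.** I simulated 50,000 trials per setting with normal change scores and applied the plan's rule of running paired tests only after a significant interaction. The interaction was significant in about 5% of trials at every drift. The chance that the interaction was significant and at least one arm's paired test was too was:
- 3.2-3.3% at no drift
- 4.4-4.9% at 1.0 point
- 4.9-5.1% at 2.0 points

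With 17 per arm (the plan's 15% dropout) the range over all drifts is 3.1-5.2%. This is the basis for about 3-5% per endpoint.

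**Step 4: the planned 3.24-point difference is real.** I added drift in the same direction to both arms and set diet's own effect to zero, so that anything found in the Diet-alone arm is drift or chance. The interaction-significant column repeats step 2; the last four columns are the percentage of trials in which the Diet-alone change is declared significant under the rule (20 per arm).

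| Variance, correlation | Interaction significant | No drift | 0.5 | 1.0 | 1.5 |
|---|---|---|---|---|---|
| 6.25, 0.70 | 99.9% | 4.9% | 19.6% | 59.3% | 90.8% |
| 6.25, 0.50 | 97.9% | 4.5% | 11.9% | 37.8% | 69.6% |
| 12.5, 0.70 | 95.4% | 4.0% | 9.8% | 30.3% | 59.9% |
| 12.5, 0.50 | 80.6% | 3.1% | 3.7% | 12.0% | 28.0% |

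The rule screens on the difference between arms. Once that difference exists, it says nothing about why the Diet-alone arm moved.

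**Step 5: regression to the mean from the entry cut.** Section 4 excludes body fat below 22%. Taking mean 35.9 and SD 6.7 from Section 3.2, item 4 (assumed to apply here), z = (22 − 35.9)/6.7 = −2.07. The expected fall is SD × (1 − correlation) × φ(z)/(1 − Φ(z)), which is 0.10 points at correlation 0.70 and 0.16 at 0.50. This source is small.

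**The case against.** The strongest defence is that the trial is comparative throughout. The lead sentence of Section 2 sets the combined programme against Diet Alone, power is for the group-by-time interaction, and the regression models change scores on group. Under that lead sentence Objective 1 can be read as the effect over diet. For bone density, lipids and hsCRP, the wording of a before-after comparison is already close to descriptive. Entry requires weight change under 5% over 12 months and injury of more than 12 months, which limits drift in weight.

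Much of this stands. A reader might infer that any drift over 16 weeks will be reported as a treatment effect. The documents do not support that: they leave interpretation open, and the paired tests are conditional. An unconditional paired test in one arm would flag a 1.0-point drift in 23-59% of trials with no arm difference, but the plan does not run that test; under its own rule the figure is about 3-5% (step 3). Nor does the position of these objectives at the top of the list show that they will be the main conclusions; neither has its own power calculation.

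What does not stand is the inference that the objectives are therefore sound. Objective 2 has no comparative reading. Weight stability does not control drift in insulin sensitivity, glucose effectiveness, BMR, lipids or hsCRP. The conditional rule protects little in the scenario the trial is planned for, and it leaves any drift in the within-arm estimate whether or not that estimate is tested.

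**Conclusion.** Wrong as written: the design cannot deliver Objective 2, and can deliver Objective 1 only for the increment from cycling. The between-arm analyses and their power are untouched.

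The practical risk depends on whether the arms differ. If they do not, common drift rarely surfaces as a significant within-arm result. If the planned difference is real, a 1.0-point common drift is called a significant Diet-alone change in 12-59% of trials at 20 per arm. That range rests on the plan's variances and correlations taken as given, normal change scores, drift equal in both arms and in the direction of benefit, and no diet effect. Larger variances would lower it. The size of drift is assumed, not documented, so this shows what the wording exposes the trial to and does not forecast what will happen. The identification problem itself depends on none of these numbers.

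**What to change.** Reword Objectives 1 and 2 to *estimate the within-arm change, with 95% CI, in* the listed variables. In the closing paragraph of Section 10, Statistical methods, add that paired tests and within-arm estimates are descriptive, and that claims of effect rest only on the between-arm contrasts of Objectives 3, 5 and 6, that is, on what FES cycling adds to diet.

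The paired tests need not be removed; labelling them is enough. Section 10 already promises the reporting needed ("level of significance. Effects will be reported with a point estimate and 95% confidence intervals").

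The cost is two objectives and one added statement, with no new subjects, visits or data. The trial gives up a stand-alone efficacy claim for Diet alone or for the combined programme. Such a claim would need an untreated arm.

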3.2 Previous Data

1. Body Composition & Energy Expenditure: A preliminary investigation in our laboratory has demonstrated the accuracy of using DXA as a proxy for 4-compartment modeling (Heymsfeld, 1990) to assess body composition in SCI adults.[26] In comparing body composition analyses techniques in 72 individuals with SCI, we recently found Total Error to be 4.8% with Dual X-ray Absorptiometry, 5.7% with hydrodensitometry, 16.0% with bioelectrical impedance analysis), and 6.2% with standard skinfold equations when compared to 4-compartment modeling, the currently accepted gold standard for body composition assessment. We also participated in a multisite trial to develop a compendium of physical activity energy expenditures for SCI, and provided significant data demonstrating reduced energy expenditure at rest and during activities when compared to AB literature.[90]

2. Prevalence of Metabolic Syndrome in Persons with SCI. We have previously reported on the incidence of obesity and hypertension in a large cohort (n=7959) of veterans with SCI in which 53% had BMI>25, and a surprising 22% had clinically significant hypertension.[27] Additionally, we conducted a nationwide survey that demonstrated diabetes prevalence is greater among veterans with an SCI/D compared with the civilian population, but similar to that of other veterans, although it may occur at a younger age in those with an SCI/D.[40] Our lab previously reported retrospective data on 477 veterans with SCI screened for metabolic syndrome using the International Diabetes criteria previously reported. Within the sample, 56.5% had BMI > 25 kg/m² , 63.4% had HDL-c < 40 mg/dl, 48.7% had fasting blood glucose > 100 mg/dl, 56.5% had hypertension, and 44.8% met criteria as having the metabolic syndrome.[91] We have recently reviewed an expanded data set of the same variables and have a manuscript in preparation with similar results.

3. Fat Mass & Glucose Tolerance: Previous work in our laboratory demonstrated a strong relationship ($r=0.67$, $p<0.001$) between body composition and glucose area under the curve following OGTT in SCI subjects at all levels of injury. Glucose AUC was more strongly correlated ($r=0.86$, $p<0.001$) with %BF in those persons with T6-L2 SC. Additional work in our laboratory (Figure 1) has demonstrated significant relationships between visceral adipose tissue (VAT) and plasma glucose levels.[92, 93] Although relationships were also demonstrated for subcutaneous abdominal adipose tissue (SAT) and plasma glucose, these were not significant. Plasma insulin was somewhat variable presumably due to the nature and longevity of the person's glucose intolerance; those with acute glucose impairments were more likely to have hyperinsulinemia. For Individuals with SCI, increases in VAT, SAT, or VAT/SAT ratio are associated with an adverse metabolic profile, manifested by impaired glucose tolerance, insulin resistance, and dyslipidemia. [92, 93]

4. OGTT & Level of SCI. In 20 non-diabetic SCI subjects tested before exercise intervention, mean % Body Fat determined by 4-compartment modeling was 35.9 ± 6.7 ,

whereas %BF for able-bodied (AB) adults generally ranges from 12-25%. Further, Glucose AUC during 3-hour OGTT was significantly elevated in C7- T5 (965 ± 102 mg%•min) and T6-L2 SCI (723 ± 52) compared to non-diabetic AB adults (679 ± 18), and significantly different from each other ($P<0.05$); see figure 2. Of note, the glucose:insulin AUC ratio, a gross measure of insulin sensitivity, appeared elevated in our SCI subjects compared to AB adults (3.68 ± 3.02 vs 1.41 ± 0.89), although not significantly so.

5. Intravenous Glucose Tolerance Test (IVGTT). [name] learned the IVGTT procedure during his VHA and NIH Career Development Awards and has been proficient performing IVGTTs for over 18 years. [name] has supervised over 150 IVGTTs in the past 4 years, and the U Miami CTSI CRC staff routinely performs IVGTTs for several of the metabolic protocols being done there. Based on our recent results from FESLCE on glucose kinetics, HBFES LCE + Diet is expected to reduce % Body Fat and improve insulin sensitivity and glucose effectiveness during intravenous glucose tolerance tests.

6. Bone Mineral Density (BMD) in SCI. We've previously demonstrated a strong relationship between time since SCI and lower extremity BMD using DXA.[94] The regional bone measurements were determined using specified region of interest (ROI) analyses specified by the DXA manufacture (Lunar DPXIQ; Software version 4.3, Madison, WI). The resulting precision of the arm, leg, and trunk BMD measurements was 0.0202, 0.0128, and 0.0086 g/cm², respectively, while % coefficient of variation of arm, leg and trunk BMD were 1.92 %, 0.86 %, and 0.86 %, respectively. Although we did not see a significant increase in BMD with our most recent FES interventional trial, it appeared that BMD remained constant or slightly increased over the 4-month intervention. We will be monitoring for similar trends in the Home-based interventional trial.

7. Novel Home Based FES (HBFES): [name] was a co-investigator on several FES trials while at the U Kentucky, U Michigan, and Virginia Commonwealth University and has authored several publications about patient selection criteria, potential complications and rate of exercise progression required for functional electrical stimulation.[95-99] He was part of a VA multi-site grant on implanted neuroprostheses for standing with the lead group at the Cleveland FES Center of Excellence, and a paper summarizing that data was recently published.[100] His group utilized FES in several protocols for paraplegia which have recently been completed and additional manuscripts are in preparation. In comparison with arm crank ergometry, paraplegic subjects assigned to the FES-LCE group demonstrated similar improvements in body composition, glucose effectiveness and insulin sensitivity. Our lab has continued to demonstrate positive body composition changes, as well as response to different FES stimulation patterns. [98, 99, 101-103]

[name] lab recently piloted a program for VACO Prosthetics and Orthotics of rent-to-purchase RT300s for veterans in whom 90-day exercise compliance with the equipment can be documented. Patients were screened by their physicians and initial exercise trials monitored in the SCI Exercise Laboratory before sending the RT300 (Restorative Therapeutics, Inc., Baltimore, MD) to the veteran's home for the 3-month trial.

Preliminary work with n=17 veterans with paraplegia over 12 months has demonstrated ease of use, ability to monitor and adjust settings by internet, and 80% successful completion by those participating. The telemedicine program has demonstrated capacity to use the VitelCare® T400 (Bosch, Vienna, VA) to monitor HR & BP during home-based exercise, and we will purchase similar systems and web cams to monitor our subjects at home. As preliminary work for the current proposal, we demonstrated improvements in several individuals with tetraplegia using HBFES 5 days/week for 1 year up to 56 months, with increased FFM and RMR, but %BF didn't decrease as expected, likely due to unmonitored dietary intake. [104, 105] Previous studies have not used persons with high SCI due to concern of autonomic dysreflexia and inability to monitor exercise in the home.

8. Novel Home Based Dietary Approach for SCI: Early in his career, [name] conducted exercise and dietary interventional studies assessing changes in body composition and glucose tolerance in able-bodied populations.[106, 107] He has utilized dietary assessments in his most recent studies, and has contributed to the sparse literature on dietary interventions for persons with SCI.[1, 5, 87-90] Of note, BMR for high SCI often falls below 1,000 Kcal/day. [name] group recently published a review article on the role of nutrition after SCI further elucidating the need for this research, [88] and another demonstrating the relative efficacy of 24-hour dietary recall in persons with SCI. [87]

3.3 Study Rationale

Spinal cord injuries (SCI) predispose individuals to impaired fitness, obesity, glucose intolerance and insulin resistance, placing them at greater risk for diabetes and coronary artery disease. These health risks are only moderately reduced with upper extremity exercise, due to the relatively small muscle mass utilized, and upper extremity exercise has very limited potential for persons with high paraplegia or tetraplegia. Functional electrical stimulation leg cycle ergometry is likely to improve whole body composition, energy expenditure and glucose metabolism. Closely monitored diet intervention may also reduce body weight but is more likely to result in loss of lean tissue, i.e., metabolically active muscle tissue, with subsequent reductions in energy metabolism and the re-accumulation of adipose tissue. Both types of interventions have been tried in institutional settings previously, but compliance has typically been an issue due to distance and environmental barriers that prevent easy access. The purpose of this proposal is to evaluate and compare the health benefits of home-based functional

IRB Study Number: 20190659

NCT03495986

Version v18 071825

electrical stimulation leg cycle ergometry plus diet (HBFESLCE + Diet) to home-based (HB) Diet alone.

4. Inclusion and Exclusion Criteria

Inclusion criteria:

- Adults 18-65 years of age (inclusive)
- Sex: male or female
- Women of child-bearing potential who agree to refrain from getting pregnant during the trial
- C4-T4 motor complete (AIS A, B & C) spinal cord injury for duration greater than 12 months
- <5% change in body weight over the past 12 months

Exclusion criteria:

- <22% body fat
- Unresponsive to neurostimulation
- Those who have participated in a FES or ACE exercise program (>60 minutes/week) within the past 3 months
- Known orthopaedic limitations
- Coronary artery disease
- Type 1 diabetes mellitus, insulin-requiring Type 2 or untreated diabetes mellitus (fasting glucose>126 or HgbA1c>7.0)
- Uncompensated Hypothyroidism (Stable on medication >1 year or not on medication)
- Renal disease
- Uncontrolled autonomic dysreflexia, recent (within 3 months)
- Deep vein thrombosis (within the past 3 months)
- Anticoagulation therapy

IRB Study Number: 20190659

NCT03495986

Version v18 071825

- Pressure ulcers > Grade II
- Decisional impairment
- Any potential causes of autonomic dysreflexia at the discretion of the PI
- Prisoners
- Pregnant or nursing women

5. Number of Subjects

Forty (40) subjects will participate in the study; however, it may be necessary to screen up to 60 subjects to allow for those who do not meet inclusion/exclusion criteria.

Study Timelines

It is anticipated that subjects will be enrolled in the study for 21 weeks.

It is anticipated that enrollment of subjects will occur between August 15, 2020 and December 31, 2024.

6. Study Endpoints

Primary Study Endpoints:

1. Body composition (%BF, FM and FFM)
2. Insulin sensitivity
3. Glucose effectiveness
